13.6.3 Subgroup analyses

Output name	Display *	Title (Description)	Analysis set(s)	Key	Mock layout
DBP_MCPMOD_AGE	T	MCP-Mod estimation of dose-response in change from baseline to Week 8 in mean trough sitting diastolic blood pressure (SiDBP) by Age	PPS		LAYMCP2

Output name	Display *	Title (Description)	Analysis set(s)	Key	Mock layout
DBP_MCPMOD _AGE	F	MCP-Mod estimation of dose-response in change from baseline to Week 8 in mean trough sitting diastolic blood pressure (SiDBP) by Age	PPS		LAYMCP6
DBP_MCPMOD _SEX	T	MCP-Mod estimation of dose-response in change from baseline to Week 8 in mean trough sitting diastolic blood pressure (SiDBP) by Sex	PPS		LAYMCP2
DBP_MCPMOD _SEX	F	MCP-Mod estimation of dose-response in change from baseline to Week 8 in mean trough sitting diastolic blood pressure (SiDBP) by Sex	PPS		LAYMCP6
DBP_MCPMOD _RACE	T	MCP-Mod estimation of dose-response in change from baseline to Week 8 in mean trough sitting diastolic blood pressure (SiDBP) by Race	PPS		LAYMCP2
DBP_MCPMOD _RACE	F	MCP-Mod estimation of dose-response in change from baseline to Week 8 in mean trough sitting diastolic blood pressure (SiDBP) by Race	PPS		LAYMCP6

* T = Summary Table; F = Figure.

MCP-Mod = Multiple Comparison Procedure – Modeling; PPS = Per-Protocol Set; SiDBP = sitting diastolic blood pressure. Age category: < 65 vs ≥ 65 years.

13.7 Secondary efficacy analyses

Output name	Display *	Title (Description)	Analysis set(s)	Key	Mock layout
SBP_VIS	T	Mean trough sitting systolic blood pressure (SiSBP) as measured by OBPM by visit and treatment group	PPS, FAS		LAYCON001
SBP_CHG	T	Change from baseline to post-baseline visits in mean trough sitting systolic blood pressure (SiSBP) as measured by OBPM by treatment group	PPS, FAS	Yes	LAYBASE001
SBP_MCHG	F	Mean change from baseline to post-baseline visits in mean trough sitting systolic blood pressure (SiSBP) as measured by OBPM by treatment group	PPS, FAS	Yes	LAYTIME
SBP_CHG	F	Density of change from baseline to post-baseline visits in mean trough sitting systolic blood pressure (SiSBP) as measured by OBPM by treatment group	PPS, FAS		LAYDENS
SBP_MCPMOD 1	T	MCP-Mod test for dose-response in change from baseline to Week 8 in mean trough sitting systolic blood pressure (SiSBP)	PPS, FAS	Yes	LAYMCP1
SBP_MCPMOD 2	T	MCP-Mod estimation of dose-response in change from baseline to Week 8 in sitting systolic blood pressure (SiSBP)	PPS, FAS	Yes	LAYMCP2

Output name	Display *	Title (Description)	Analysis set(s)	Key	Mock layout
SBP_MCPMO D	F	MCP-Mod estimation of dose-response in change from baseline to Week 8 in sitting systolic blood pressure (SiSBP)	PPS, FAS		LAYMCP3
SBP_MCPMO D_SEL	F	MCP-Mod estimation of response at study doses in change from baseline to Week 8 in mean trough sitting systolic blood pressure (SiSBP) - Best fitting model	PPS, FAS	Yes	LAYMCP4
SBP_MCPMO D_SEL	F	MCP-Mod estimation of response at study doses in change from baseline to Week 8 in mean trough sitting systolic blood pressure (SiSBP) - Best fitting model	PPS, FAS		LAYMCP5
SBP_ANCOVA	T	ANCOVA for change from baseline to Week 8 in mean trough sitting systolic blood pressure (SiSBP) - ACT-132577 vs placebo	PPS, FAS	Yes	LAYBETW00 1
SBP_ANCOVA	F	ANCOVA for change from baseline to Week 8 in mean trough sitting systolic blood pressure (SiSBP) - ACT-132577 vs placebo	PPS, FAS	Yes	LAYFOR
SBP_ANCOVA _L	T	ANCOVA for change from baseline to Week 8 in mean trough sitting systolic blood pressure (SiSBP) - Lisinopril vs placebo	PPS, FAS	Yes	LAYBETW00 1

Output name	Display *	Title (Description)	Analysis set(s)	Key	Mock layout
SBP_MIXED_W2_W4_W8	T	Mixed Model for changes from baseline to Weeks 2, 4 and 8 in sitting systolic blood pressure (SiSBP, OC) - ACT-132577 vs placebo	FAS		LAYBETW001
SBP_MIXED_W2_W4_W8_MCP1	T	Mixed Model for changes from baseline to Weeks 2, 4 and 8 in sitting systolic blood pressure (SiSBP, OC) - MCP-Mod test for dose-response at Week 8	FAS		LAYMCP1
SBP_MIXED_W2_W4_W8_MCP2	T	Mixed Model for changes from baseline to Weeks 2, 4 and 8 in sitting systolic blood pressure (SiSBP, OC) - MCP-Mod estimation of dose-response at Week 8	FAS		LAYMCP2
SBP_MIXED_W2_W4_W8_L	T	Mixed Model for changes from baseline to Weeks 2, 4 and 8 in mean trough sitting systolic blood pressure (SiSBP, OC) - Lisinopril vs placebo	FAS		LAYBETW001
SBP_MIXED_AVER8	T	Mixed Model for changes from baseline to Weeks 2, 4 and 8 in sitting systolic blood pressure (SiSBP, OC) - ACT-132577 vs placebo	PPS, FAS		LAYBETW001

Output name	Display *	Title (Description)	Analysis set(s)	Key	Mock layout
SBP_MIXED_AVER8_MCP1	T	Mixed Model for average change from baseline to Weeks 2, 4 and 8 in sitting systolic blood pressure (SiSBP, OC) - MCP-Mod test for dose-response	PPS, FAS		LAYMCP1
SBP_MIXED_AVER8_MCP2	T	Mixed Model for average change from baseline to Weeks 2, 4 and 8 in sitting systolic blood pressure (SiSBP, OC) - MCP-Mod estimation of dose-response	PPS, FAS		LAYMCP2
SBP_MIXED_AVER8_L	T	Mixed Model for average change from baseline to Weeks 2, 4 and 8 in mean trough sitting systolic blood pressure (SiSBP, OC) - Lisinopril vs placebo	PPS, FAS		LAYBETW00 1
SBP_MCPMOD_AGE	T	MCP-Mod estimation of dose-response in change from baseline to Week 8 in mean trough sitting systolic blood pressure (SiSBP) by Age	PPS		LAYMCP2
SBP_MCPMOD_AGE	F	MCP-Mod estimation of dose-response in change from baseline to Week 8 in mean trough sitting systolic blood pressure (SiSBP) by Age	PPS		LAYMCP6
SBP_MCPMOD_SEX	T	MCP-Mod estimation of dose-response in change from baseline to Week 8 in mean trough sitting systolic blood pressure (SiSBP) by Sex	PPS		LAYMCP2

Output name	Display *	Title (Description)	Analysis set(s)	Key	Mock layout
SBP_MCPMOD _SEX	F	MCP-Mod estimation of dose-response in change from baseline to Week 8 in mean trough sitting systolic blood pressure (SiSBP) by Sex	PPS		LAYMCP6
SBP_MCPMOD _RACE	T	MCP-Mod estimation of dose-response in change from baseline to Week 8 in mean trough sitting systolic blood pressure (SiSBP) by Race	PPS		LAYMCP2
SBP_MCPMOD _RACE	F	MCP-Mod estimation of dose-response in change from baseline to Week 8 in mean trough sitting systolic blood pressure (SiSBP) by Race	PPS		LAYMCP6
COR_DBP_SB P	F	Correlation between change from baseline in Diastolic and Systolic Blood Pressure by Visit and Treatment Group	PPS		LAYCORR
CRR_DBP	T	Control and response rates at Week 8 for sitting diastolic blood pressure (SiDBP) as measured by OBPM	PPS		LAYCAT002
CR_DBP_LOG REG1	T	Logistic regression for control rates at Week 8 for sitting diastolic blood pressure (SiDBP) as measured by OBPM < 90 mmHg	PPS		LAYLOGR

Output name	Display *	Title (Description)	Analysis set(s)	Key	Mock layout
CR_DBP_LOG REG2	T	Logistic regression for control rates at Week 8 for sitting diastolic blood pressure (SiDBP) as measured by OBPM < 85 mmHg	PPS		LAYLOGR
CR_DBP_LOG REG_MCP1	T	Logistic regression for control rates at Week 8 for sitting diastolic blood pressure (SiDBP) as measured by OBPM < 90 mmHg - MCP-Mod test for dose-response	PPS		LAYMCP1
CR_DBP_LOG REG_MCP2	T	Logistic regression for control rates at Week 8 for sitting diastolic blood pressure (SiDBP) as measured by OBPM < 90 mmHg - MCP-Mod estimation of dose-response	PPS		LAYMCP2
RR_DBP_LOG REG	T	Logistic regression for response rates at Week 8 for sitting diastolic blood pressure (SiDBP) as measured by OBPM	PPS		LAYLOGR
CRR_SBP	T	Control and response rates at Week 8 for sitting systolic blood pressure (SiSBP) as measured by OBPM	PPS		LAYCAT002
CR_SBP_LOG REG1	T	Logistic regression for control rates at Week 8 for sitting systolic blood pressure (SiSBP) as measured by OBPM < 140 mmHg	PPS		LAYLOGR

Output name	Display *	Title (Description)	Analysis set(s)	Key	Mock layout
CR_SBP_LOG REG2	T	Logistic regression for control rates at Week 8 for sitting systolic blood pressure (SiSBP) as measured by OBPM < 135 mmHg	PPS		LAYLOGR
CR_SBP_LOG REG_MCP1	T	Logistic regression for control rates at Week 8 for sitting systolic blood pressure (SiSBP) as measured by OBPM < 140 mmHg - MCP-Mod test for dose-response	PPS		LAYMCP1
CR_SBP_LOG REG_MCP2	T	Logistic regression for control rates at Week 8 for sitting systolic blood pressure (SiSBP) as measured by OBPM < 140 mmHg - MCP-Mod estimation of dose-response	PPS		LAYMCP2
RR_SBP_LOG REG	T	Logistic regression for response rates at Week 8 for sitting systolic blood pressure (SiSBP) as measured by OBPM	PPS		LAYLOGR
24H_DBP_CH G	T	Change from baseline to Week 8 in 24-hour mean diastolic blood pressure (DBP) as measured by ABPM by treatment group	PPS		LAYBASE00 1
24H_DBP_AN COVA	T	ANCOVA for change from baseline to Week 8 in 24-hour mean diastolic blood pressure (DBP) as measured by ABPM - ACT-132577 vs Placebo	PPS	Yes	LAYBETW00 1

Output name	Display *	Title (Description)	Analysis set(s)	Key	Mock layout
24H_DBP_ANCOVA_L	T	ANCOVA for change from baseline to Week 8 in 24-hour mean diastolic blood pressure (DBP) as measured by ABPM - Lisinopril vs Placebo	PPS	Yes	LAYBETW001
24H_SBP_CHG	T	Change from baseline to Week 8 in 24-hour mean systolic blood pressure (SBP) as measured by ABPM by treatment group	PPS		LAYBASE001
24H_SBP_ANCOVA_L	T	ANCOVA for change from baseline to Week 8 in 24-hour mean systolic blood pressure (SBP) as measured by ABPM - Lisinopril vs Placebo	PPS	Yes	LAYBETW001
OBPM	L	Listing of mean trough sitting diastolic (SiDBP), mean trough sitting systolic blood pressure (SiSBP) and pulse rate measured by OBPM with control and response rates	FAS		L_OBPM
ABPM24_DBP_BAS	F	Mean diastolic blood pressure (DBP) per hour as measured by ABPM at baseline	PPS		LAY_ABPM
ABPM24_DBP_WK8	F	Mean diastolic blood pressure (DBP) per hour as measured by ABPM at Week 8	PPS		LAY_ABPM

Output name	Display *	Title (Description)	Analysis set(s)	Key	Mock layout
ABPM24_DBP_WK8_DIF	F	Difference in mean diastolic blood pressure (DBP) per hour as measured by ABPM	PPS		LAY_ABPM
ABPM24_DBP_TTPR	T	Trough to peak ratio for diastolic blood pressure (DBP) measured by ABPM	PPS		LAY_TTPR
ABPM24_SBP_BAS	F	Mean systolic blood pressure (SBP) per hour as measured by ABPM at baseline	PPS		LAY_ABPM
ABPM24_SBP_WK8	F	Mean systolic blood pressure (SBP) per hour as measured by ABPM at Week 8	PPS		LAY_ABPM
ABPM24_SBP_WK8_DIF	F	Difference in mean systolic blood pressure (SBP) per hour as measured by ABPM	PPS		LAY_ABPM
ABPM24_SBP_TTPR	T	Trough to peak ratio for systolic blood pressure (SBP) measured by ABPM	PPS		LAY_TTPR

* T = Summary Table; F = Figure.

ABPM = ambulatory blood pressure monitoring; ANCOVA = analysis of covariance; DBP = diastolic blood pressure; FAS = Full Analysis Set; MCP-Mod = Multiple Comparison Procedure – Modeling; OBPM = automated office blood pressure measurement; PPS = Per-Protocol Set; SBP = systolic blood pressure; SiDBP = sitting diastolic blood pressure; SiSBP = sitting systolic blood pressure.

ABPM analyses are based on the subset of the PPS described in Section 5.5.

Age category: < 65 vs ≥ 65 years.

13.8 Other efficacy analyses

Output name	Display *	Title (Description)	Analysis set(s)	Key	Mock layout
DAY_DBP_CHG	T	Change from baseline to Week 8 in 24-hour mean daytime diastolic blood pressure (DBP) as measured by ABPM by treatment group	PPS		LAYBASE001

Output name	Display *	Title (Description)	Analysis set(s)	Key	Mock layout
DAY_DBP_ANCOVA	T	ANCOVA for change from baseline to Week 8 in mean daytime diastolic blood pressure (DBP) as measured by ABPM	PPS		LAYBETW001
NIGHT_DBP_CHG	T	Change from baseline to Week 8 in 24-hour mean night time diastolic blood pressure (DBP) as measured by ABPM by treatment group	PPS		LAYBASE001
NIGHT_DBP_ANCOVA	T	ANCOVA for change from baseline to Week 8 in mean night time diastolic blood pressure (DBP) as measured by ABPM	PPS		LAYBETW001
DAY_SBP_CHG	T	Change from baseline to Week 8 in 24-hour mean daytime systolic blood pressure (DBP) as measured by ABPM by treatment group	PPS		LAYBASE001
DAY_SBP_ANCOVA	T	ANCOVA for change from baseline to Week 8 in mean daytime systolic blood pressure (SBP) as measured by ABPM	PPS		LAYBETW001
NIGHT_SBP_CHG	T	Change from baseline to Week 8 in 24-hour mean night time systolic blood pressure (SBP) as measured by ABPM by treatment group	PPS		LAYBASE001

Output name	Display *	Title (Description)	Analysis set(s)	Key	Mock layout
NIGHT_SBP _ANCOVA	T	ANCOVA for change from baseline to Week 8 in mean night time systolic blood pressure (SBP) as measured by ABPM	PPS		LAYBETW0 01
MIXED_DB P_W2_W4_ W8_W10	T	Mixed model for changes from baseline to Weeks 2, 4, 8 and 10 in mean trough sitting diastolic blood pressure (SiDBP, OC) as measured by OBPM	PPS		LAYBETW0 01
MIXED_SBP _W2_W4_W 8_W10	T	Mixed model for changes from baseline to Weeks 2, 4, 8 and 10 in mean trough sitting systolic blood pressure (SiSBP, OC) as measured by OBPM	PPS		LAYBETW0 01
ABPM	L	Listing of individual diastolic and systolic blood pressure measured by ABPM	FAS		LSTCSR09 32
DN_ABPM	L	Listing of 24-hour mean, daytime mean and night time mean diastolic and systolic blood pressure measured by ABPM	FAS		LSTCSR09 32

* T = Summary Table; L = Listing.

ABPM = ambulatory blood pressure monitoring; ANCOVA = analysis of covariance; DBP = diastolic blood pressure; FAS = Full Analysis Set; MCP-Mod = Multiple Comparison Procedure – Modeling; OBPM = automated office blood pressure measurement; PPS = Per-Protocol Set; SBP = systolic blood pressure; SiDBP = sitting diastolic blood pressure; SiSBP = sitting systolic blood pressure.

ABPM analyses are based on the subset of PPS subjects describe d in Section 5.5.

13.9 Safety analyses

13.9.1 Adverse events

Output name	Display *	Title (Description)	Analysis set(s)	Key	Mock layout
AEOV	T	Overview of double-blind treatment-emergent adverse events (AEs)	SAF	Yes	LAYAE004
TEAESCPR	T	Double-blind treatment-emergent adverse events (AEs) by primary system organ class (SOC) and preferred term	SAF		LAYAE001
TEAEPR	T	Double-blind treatment-emergent adverse events (AEs) by preferred term	SAF		LAYAE002
TEAERESCP R	T	Double-blind treatment-emergent adverse events (AEs) related to study treatment by primary system organ class (SOC) and preferred term	SAF		LAYAE001
TEAEREPR	T	Double-blind treatment-emergent adverse events (AEs) related to study treatment by preferred term	SAF		LAYAE002
TEAEPRIN	T	Double-blind treatment-emergent adverse events (AEs) by maximum intensity	SAF		LAYAE003
AEOV	T	Overview of run-in treatment-emergent adverse events (AEs)	RIS		LAYAE004
TEAEPR	T	Run-in treatment-emergent adverse events (AEs) by preferred term	RIS		LAYAE002

Output name	Display *	Title (Description)	Analysis set(s)	Key	Mock layout
AE	L	Listing of adverse events (AEs)	RIS		LSTCSR071

* T = Summary Table; L = Listing.
AE = adverse event; RIS = Run-in Set; SAF = Safety Set.

13.9.2 Deaths

Output name	Display *	Title (Description)	Analysis set(s)	Key	Mock layout
DEATH	L	Listing of deaths	SAF		LSTCSR072

* L= Listing,
SAF=Safety set.

13.9.3 Serious adverse events

Output name	Display *	Title (Description)	Analysis set(s)	Key	Mock layout
TESAESCPR	T	Double-blind treatment-emergent serious adverse events (SAEs) by primary system organ class (SOC) and preferred term	SAF	Yes	LAYAE001
TESAEPR	T	Double-blind treatment-emergent serious adverse events (SAEs) by preferred term	SAF		LAYAE002
TESAERESCPR	T	Double-blind treatment-emergent serious adverse events (SAEs) related to study treatment by preferred term	SAF		LAYAE002

Output name	Display *	Title (Description)	Analysis set(s)	Key	Mock layout
TESAEPR	T	Run-in treatment-emergent serious adverse events (SAEs) by preferred term	RIS		LAYAE002
SAE	L	Listing of serious adverse events (SAEs)	RIS		LSTCSR071

* T = Summary Table; L = Listing.

RIS = Run-in Set; SAE = serious adverse event; SAF = Safety Set; SOC = system organ class.

13.9.4 Adverse events leading to treatment discontinuation

Output name	Display *	Title (Description)	Analysis set(s)	Key	Mock layout(AEs)
TEAEPDSCPR	T	Double-blind treatment-emergent adverse events (AEs) leading to premature discontinuation of study treatment by primary system organ class (SOC) and preferred term	SAF	Yes	LAYAE001
TEAEPDPR	T	Double-blind treatment-emergent adverse events (AEs) leading to premature discontinuation of study treatment by preferred term	SAF		LAYAE002
TEAEPDPR	T	Run-in treatment-emergent adverse events (AEs) leading to premature discontinuation of study treatment by preferred term	RIS		LAYAE002
AEPD	L	Listing of adverse events (AEs) leading to premature discontinuation of study treatment	SCR		LSTCSR071

* T = Summary Table; L = Listing.

AE = adverse event; RIS = Run-in Set; SAF = Safety Set; SOC = system organ class.

13.10 Electrocardiogram (ECG)

Output name	Display *	Title (Description)	Analysis set(s)	Key	Mock layout
ECG_CHG	T	ECG parameters: changes from baseline to end of double-blind treatment	SAF		LAYBASE001
ECGQTCP T	T	Number of subjects with double-blind treatment-emergent ECG abnormalities (based on Fridericia's formula)	SAF		LAYECG001
ECGMA	L	Listing of 12-lead ECG variables in subjects with at least one double-blind treatment-emergent ECG abnormalities	SAF		LSTCSR0931
ECG	L	Listing of 12-lead ECG variables and abnormalities	SCR		LSTCSR093

* T = Summary Table; L = Listing.
ECG = electrocardiogram; SAF = Safety Set; SCR = Screened Set.

13.11 Laboratory tests

Output name	Display*	Title (Description)	Analysis set(s)	Key	Mock layout
HEMAV_VIS	T	Hematology parameters: absolute values by visit	SAF		LAYLAB003a
HEM_CHG	T	Hematology parameters: changes from baseline to post-baseline visits	SAF	Yes	LAYLAB002a

Output name	Display*	Title (Description)	Analysis set(s)	Key	Mock layout
HEM_CHG	F	Mean change from baseline to post- baseline visits in hemoglobin by treatment group	SAF		LAYTIME
CHEAV_VIS	T	Chemistry parameters: absolute values by visit	SAF		LAYLAB003a
CHE_CHG	T	Chemistry parameters: changes from baseline to post-baseline visits	SAF		LAYLAB002a
UACRAV_VIS	T	Urine parameter: UACR absolute values by visit	SAF		LAYLAB003a
UACR_CHG	T	Urine parameter: UACR changes from baseline to post-baseline visits	SAF	Yes	LAYLAB002a
	T	Definition of abnormal laboratory values	NA		
HEM_TEMA	T	Hematology parameters: treatment-emergent marked abnormalities	SAF		LAYLAB001
CHE_TEMA	T	Chemistry parameters: treatment-emergent marked abnormalities	SAF		LAYLAB001
CHE_ALT_BIL	T	Number of subjects with ALT > 3 × ULN and bilirubin > 2 × ULN	SAF		LAYCAT002

Output name	Display*	Title (Description)	Analysis set(s)	Key	Mock layout
LABMLA	L	Listing of definitions of marked laboratory abnormality	-		L_LABMLA
LAB	L	Listing of individual laboratory measurements (SI units)	SCR		LSTCSR081
HEM_CHG	F	Density of change from baseline to post-baseline visits in hemoglobin by treatment group	SAF		LAYDENS
HEM_MCPMOD1	T	MCP-Mod test for dose-response in change from baseline to Week 8 in hemoglobin	SAF		LAYMCP1
HEM_MCPMOD2	T	MCP-Mod estimation of dose-response in change from baseline to Week 8 in hemoglobin	SAF		LAYMCP2
HEM_MCPMOD	F	MCP-Mod estimation of dose-response in change from baseline to Week 8 in hemoglobin	SAF		LAYMCP3

* T = Summary Table; L = Listing; F = Figure.

ALT = alanine aminotransferase; MCP-Mod = Multiple Comparison Procedure – Modeling; SAF = Safety Set; SCR = Screened Set; SI = Standard International; UACR = urine albumin-to-creatinine ratio; ULN = upper limit of normal; NA = not applicable.

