5.1.12 Study-specific criteria for interruption / premature discontinuation of study treatment

A) Hypertension

At any time throughout the study if mean SiDBP \geq 110 mmHg and/or mean SiSBP \geq 180 mmHg is measured by OBPM, i.e., essential hypertension grade 3 [Mancia 2013], BP must be re-measured. If the value (i.e., mean SiSBP \geq and/or DBP \geq 110 mmHg measured by OBPM at the site) is confirmed, subject must permanently discontinue study treatment.

The BP re-measurement can be during the same visit (e.g., within 1 h), or at the next planned visit, or at an unscheduled visit. The time of re-measurement is at investigator's discretion, taking into consideration the subject's medical history.

B) Pregnancy

If a female subject becomes pregnant while on study treatment, study treatment must be discontinued immediately, and a Pregnancy Form must be completed [see Section 10.3].

C) Liver aminotransferases abnormalities

Interruption of study treatment

After randomization study treatment must be interrupted in the following cases:

• Aminotransferases (i.e., ALT and/or AST) ≥ 3 and $\leq 8 \times ULN$

Perform a re-test of aminotransferases (ALT and AST), total and direct bilirubin, and alkaline phosphatase within 48 h. If AST and/or ALT elevation is confirmed, the re-introduction of study treatment is not to be considered.

Interruptions must be for less than 5 consecutive days; longer interruptions must lead to permanent discontinuation of study treatment [see Section 5.1.10].

Aminotransferases, total and direct bilirubin, and alkaline phosphatase levels must be monitored weekly after study drug discontinuation until values return to pre-treatment levels or within normal ranges.

Permanent discontinuation of study treatment

Study treatment must be stopped and its re-introduction is not to be considered in the following cases:

- Aminotransferases > 8 × ULN.
- Aminotransferases ≥ 3 × ULN and associated clinical symptoms of liver injury, e.g., nausea, vomiting, fever, abdominal pain, jaundice, unusual lethargy or fatigue, flu like syndrome (arthralgia, myalgia, fever).

Essential hypertension Protocol AC-080A201 Version 3 30 May 2016, page 51/112

Confidential

• Aminotransferases $\geq 3 \times \text{ULN}$ and associated increase in total bilirubin $\geq 2 \times \text{ULN}$.

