Appendix 2 Central laboratory alert flags

On top of the flags described below, at a minimum, results above the upper limit or below the lower limit of the reference range for normal subjects will be flagged.

• Exclusionary alert value – at Screening (Visit 1), and Visit 3: The result is outside the study-specific defined limit for inclusion in the study.

Hemoglobin < 100 g/L

 $AST > 3 \times ULN$

 $ALT > 3 \times ULN$

Creatinine \geq 2.26 mg/dl (200 μ mol/L) or creatinine clearance \leq 30 mL/min/1.73 m² Serum pregnancy test positive.

- Total bilirubin flag alert value all visits except Screening (Visit 1): In combination with ALT and/or AST ≥ 3 × ULN, study medication should be stopped if: Total bilirubin ≥ 2 × ULN.
- Permanent discontinuation of study medication all visits except Screening (Visit 1): Please refer to the study protocol Section 5.1.11. Study medication must be stopped if:

 $AST > 8 \times ULN, ALT > 8 \times ULN$

Serum pregnancy test positive

Hemoglobin < 80 g/L

Hemoglobin > 50 g/L decrease from baseline.

• Repeat alert value – all visits after Randomization (Visit 4): Repeat testing is needed (+ interrupt study medication if ALT and/or AST > 3 × ULN) if:

 $AST > 3 \times ULN$

 $ALT \ge 3 \times ULN$

Hemoglobin > 20 g/L decrease from baseline

Essential hypertension Protocol AC-080A201 Version 3 30 May 2016, page 110/112

Confidential

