10.9.4.1 Treatment-emergent marked laboratory abnormalities

For each category (i.e., LL, LLL, HH, HHH, HHHH), treatment-emergent marked laboratory abnormalities [see definition in Section 5.6.8.1] will be summarized by treatment group, displaying counts and percentages of subjects with at least a treatment-emergent marked laboratory abnormality for each parameter for which the marked abnormality is defined. Values from unscheduled visits are included. Subjects may be included in more than one category for the same parameter.

In addition, the number of patients with $ALT > 3 \times$ upper limit of normal (ULN) and bilirubin $> 2 \times$ ULN will be tabulated by treatment group and time point (baseline, Week 8).

Percentages are calculated as number of subjects with at least one abnormality for the parameter under consideration divided by the number of subjects with any post-baseline laboratory measurement.

The distribution of the changes from baseline in hemoglobin will be plotted for each post-baseline visit. As an exploratory analysis, dose trends in the change from baseline to Week 8 in hemoglobin will be analyzed using the MCP-Mod approach. The active comparator will be excluded from these analyses.

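### The only by-arm table joining an aminotransferase with bilirubin counts ALT alone, so a joint elevation reached through AST is not counted as a joint case

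*SAP*

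**What the plan says.** **SAP.** Section 10.9.4.1 adds a count to the marked-abnormality summaries: ALT above 3 × "upper limit of normal (ULN) and bilirubin" above 2 × ULN. It "will be tabulated by treatment group and time point (baseline, Week 8"). The output list in Section 13.11 names this table CHE_ALT_BIL, on the Safety Set, with the title "Number of subjects with ALT > 3 × ULN and bilirubin > 2 × ULN". AST appears in neither place. Section 4.1.3, which lists changes to the safety analysis, does not mention the choice of enzyme.

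**Protocol.** Section 5.1.12 C spells out its enzyme term as "Aminotransferases (i.e., ALT and/or AST"). Its permanent-discontinuation rule opens "Study treatment must be stopped and its re-introduction is not to be considered in the following cases", and one listed case is aminotransferases at or above 3 × ULN "and associated increase in total bilirubin" to at least 2 × ULN. Appendix 2 states the same pair as a laboratory alert: "In combination with ALT and/or AST ≥ 3 × ULN, study medication should be stopped if" total bilirubin is at or above 2 × ULN.

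**The concern.** The two documents describe a joint aminotransferase and bilirubin elevation in different terms. In the protocol either enzyme suffices; in the SAP table only ALT does. A zero in one arm of CHE_ALT_BIL could be taken to mean that nobody in that arm had a joint elevation, although a subject there met the protocol's joint criterion through AST. The trial compares the safety of four doses ahead of Phase 3. If such events are few, one uncounted subject could be the difference between 0 and 1 in an arm.

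**Working it through.** No sample size, power or error-rate figure bears on this point, and the plan gives no count to reproduce. The check compares definitions.

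**Inputs**
- Protocol criterion (5.1.12 C, Appendix 2): (ALT or AST) ≥ 3 × ULN and total bilirubin ≥ 2 × ULN, applied whenever it occurs after randomization.
- SAP table (10.9.4.1, 13.11): ALT > 3 × ULN and bilirubin > 2 × ULN, at baseline and Week 8.
- Week 8 window (SAP 11.1, Table 5): Day 43 to end of treatment.
- Treatment-emergent window for marked abnormalities (SAP 5.6.8.1): after the start of double-blind treatment up to its end plus 30 days, unscheduled assessments included.

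**Hypothetical cases** (multiples of ULN)

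| Case | Protocol criterion met | Table as planned | AST added only | AST added, 5.6.8.1 window |
|---|---|---|---|---|
| (a) AST 4, ALT 2, bilirubin 2.5, at Week 8 | yes | not counted | counted | counted |
| (b) ALT 4, any AST, bilirubin 2.5, at Week 8 | yes | counted | counted | counted |
| (c) ALT exactly 3, AST not above 3, bilirubin exactly 2, at Week 8 | yes | not counted | not counted | counted only with ≥ limits |
| (d) ALT 4, bilirubin 2.5, at Week 2 or 4, then stopped | yes | not counted | not counted | counted |
| (e) AST 4, ALT 2, bilirubin 2.5, at Week 2 or 4, then stopped | yes | not counted | not counted | counted |

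Case (a) isolates the enzyme gap. Cases (d) and (e) show that the time points matter too: treatment that ends before Day 43 leaves the Week 8 window empty, so such a subject is absent whichever enzyme is used. Case (c) isolates the strict inequality.

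**Do other outputs supply the joint count?** In the Section 13.11 list:
- CHE_TEMA tabulates AST (> 3, > 5, > 8 × ULN) and bilirubin (> 2, > 5 × ULN) by arm, one parameter at a time. It cannot show that both elevations occurred in the same subject.
- CHE_CHG gives changes from baseline by parameter.
- LAB lists individual values, from which the joint count could be rebuilt by hand.

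No planned output other than CHE_ALT_BIL joins an aminotransferase with bilirubin by arm, and none joins AST with bilirubin.

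**The case against.** Much of the case on the other side stands.

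- **Purpose of the table.** A reader might infer that CHE_ALT_BIL is meant to display the stopping criterion, or that it is the table for comparing doses. The documents say neither. Section 10.9.4.1 does not cite protocol 5.1.12, the output is not marked Key, and protocol 11.3.5.2 plans no joint table. It is an SAP addition, so no protocol analysis commitment is broken.
- **Strict limits.** The > 3 and > 2 × ULN limits are the SAP's own HH thresholds (Table 2, copied from protocol Appendix 1). They follow the marked-abnormality convention and are not an error in themselves.
- **Phase 1.** A reader might cite the liver case in protocol 1.2.1 as an example of what would be missed. It is not one: ALT reached 3.8 and AST 2.5 × ULN, so ALT led, and no bilirubin rise is reported there. The documents describe no AST-led case.
- **Visibility.** An AST-led subject still appears by arm in CHE_TEMA through the single parameters. Liver abnormalities leading to interruption or discontinuation must be recorded as adverse events (protocol 5.1.12 C), and adverse events leading to discontinuation are tabulated by arm in a Key output (TEAEPDSCPR).
- **Subject protection.** The stopping rule and the laboratory alert already use either enzyme, and nothing says the liver board relies on this table.

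These points limit the consequence. They do not remove the mismatch: the one table that counts joint elevations leaves out one of the two enzymes the protocol uses, with no reason given.

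**Conclusion.** The point holds as a reporting gap. CHE_ALT_BIL does not count a joint elevation reached through AST alone, and no other planned by-arm output does. The gap is confined to subjects whose ALT is not above 3 × ULN. Its size in subjects cannot be computed, because the documents give no liver event rates; the statement that one subject could change an arm from 0 to 1 assumes that such events are rare.

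The documents do not support reading this as a safety failure during the trial, as loss of data, or as a threat to the primary analysis. It is a minor but worthwhile correction to a descriptive table. Adding AST alone would be incomplete, because any subject stopped before Day 43 would remain uncounted.

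**What to change.** In SAP 10.9.4.1 and CHE_ALT_BIL:

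1. Change the condition to (ALT or AST) with total bilirubin, keeping ALT-only as a sub-row if wanted, or state why AST is left out.
2. Count the joint event at any post-baseline assessment up to the end of double-blind treatment plus 30 days, the window in 5.6.8.1. State whether both elevations must come from the same assessment, since the count would no longer be tied to one visit.
3. Either use the protocol's ≥ limits or add a footnote that > follows the marked-abnormality convention.

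The cost is a few lines of SAP text and code. AST is already in the central-laboratory chemistry panel (SAP 5.6.8), so no new data are needed. The change concerns reporting only and leaves the clinical stopping rule as it is.
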